4. STATISTICAL ANALYSES

4.1. General Considerations

4.1.1. General Methodology

Participants who prematurely withdraw from study may be replaced.

Unless otherwise specified, the Screened, Enrolled, Randomised or Safety Analysis Sets will be used for all Study Population analyses, the Safety Analysis Set will be used for all Safety analyses, the PK Analysis Set will be used for all Pharmacokinetic analyses and the PD Analysis Set will be used for all Pharmacodynamic/ Biomarker analyses.

For all summaries, statistical analyses and plots, Placebo participants will be pooled across all cohorts in which the endpoint was collected, except for the following endpoints:

- Cellular Biomarkers, CCI [REDACTED] and CCI [REDACTED] (Section 4.4.3): Placebo data will be pooled across Cohorts 1,2,3,4 and 7 CCI [REDACTED]
[REDACTED]
[REDACTED].
- CCI [REDACTED] Placebo data will be summarised by cohort since there are limited timepoints relative to the CCI [REDACTED] which are common to these cohorts.

CCI [REDACTED]
[REDACTED]
[REDACTED]

CCI [REDACTED]
[REDACTED]

Absolute baseline values will be included in all change from baseline or ratio to baseline summaries. Line plots will be produced on absolute values unless otherwise specified.

95% equal tailed Credible Intervals (CrI) will be used for statistical analyses unless otherwise specified.

Summary tables will provide the following descriptive statistics as a minimum, unless otherwise specified:

- For continuous untransformed data (or where many zeros exist in the data): n, mean, 95% Confidence Intervals (CI), standard deviation (SD), median, minimum and maximum. Number of Zeros may also be added as an additional statistic, if deemed appropriate.
- For continuous log-normally distributed data: n, geometric mean, 95% CI of the geometric mean, standard deviation on the log scale (SD (log)), %CVb (only for PK Parameters), median, minimum and maximum.
- For categorical data: number and percentage of participants in each category.

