4.3.3.2. Main analytical approach

It is assumed that endpoints defined in Section 4.3.3.1 are log_e normally distributed, unless distributional properties suggest otherwise.

The absolute values for the endpoints mentioned in Section 4.3.3.1 will be summarized descriptively. Line plots of the unadjusted geometric means and corresponding 95% CIs will be presented over time. Individual participant plots of the raw values over time will be presented by study intervention.

A Bayesian Mixed Model Repeated Measures (MMRM) analysis for the pooled placebo data across all cohorts and all doses of GSK3888130B will be fitted for Bcl-2 expression in T cells (MdFI) endpoint.

Non-informative priors will be used in this analysis. The prior for the regression coefficients will be normally distributed with mean 0 and a variance of 10⁶. Should there be convergence issues due to relatively small data values, the latter may be reduced to 10⁴. The variance-covariance matrix will use an inverse-Wishart prior distribution, consisting of the identity matrix and the degrees of freedom set to the number of visits included in the model. Sensitivity to changes in the degrees of freedom will be considered.

Terms in the model are specified below:

- Response: Absolute value on \log_e scale.
- Category: Study intervention, Visit.
- Interaction: Study intervention*Visit.
- Repeated: Visit.

Baseline values will be included in the response for this model, with visit = 'Baseline' and a distinct arbitrary code assigned for study intervention (the same for all baseline visits).

The following will be calculated from the model:

- For Baseline: The posterior mean for \log_e transformed Bcl-2,
- For each study intervention: The posterior means for \log_e transformed Bcl-2 for each post-baseline visit,
- For each study intervention: The posterior means for the difference from baseline for \log_e transformed Bcl-2 for each post-baseline visit,
- For each active study intervention: The posterior means for the difference from placebo for \log_e transformed Bcl-2 (GSK3888130B XX mg – Pooled placebo across cohorts) for each post-baseline visit.

These values will then be back transformed and the following presented:

- For Baseline: The posterior geometric mean,
- For each study intervention: The posterior geometric means for each post-baseline visit,
- For each study intervention: The posterior geometric means of the ratio to baseline for each post-baseline visit,

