- For each active study intervention: The posterior geometric means of the ratio of each active dose to placebo for each post-baseline visit.

Equal tailed 95% credible intervals will be presented for each of the above back transformed values. In addition, the posterior probability that posterior ratios of each active dose to placebo are less than ($<$) **cci** will be calculated. A line plot of the adjusted posterior geometric means and credible intervals over time will be presented.

Dose Response Modelling

If deemed appropriate, the following dose-response models will be fitted for maximum change from baseline on a \log_e scale (Max Δ) for Bcl-2 expression in T cells (MdFI) endpoint. In order to incorporate data from both SC and IV cohorts, the estimated bioavailability will be taken into account. This bioavailability estimate will be provided by CPMS following instream PK analysis, utilising data up to and including Cohort 6 data, prior to the end of study database lock (DBL).

- Four-parameters sigmoid Emax model is defined as,

$$\text{Max } \Delta(\text{Bcl-2 expression in T cells}) = (E_o + X\beta_1) + (E_{max} + X\beta_2) * \left(\frac{dose^h}{ED_{50}^h + dose^h} \right) + \epsilon$$

- Three-parameters E_{max} model is defined as,

$$\text{Max } \Delta(\text{Bcl-2 expression in T cells}) = (E_0 + X\beta_1) + (E_{\max} + X\beta_2) * \left(\frac{\text{dose}}{ED_{50} + \text{dose}} \right) + \epsilon$$

Where -

X is the continuous baseline value of Bcl-2 expression in T cells (log_e scale),

E₀ is the minimum dose effect (placebo) (log_e scale),

E_{max} is maximum achievable effect above E₀ (log_e scale),

ED₅₀ is the dose which produces half of E_{max},

h is hill parameter determining the steepness of the dose response curve,

ε is random error assumed to be normally distributed with mean zero and constant variance (σ^2)

The final model will be selected based on the best fit to the data.

Non-informative priors will be used in the analysis. The prior for E₀, E_{max}, β_1 and β_2 will be normally distributed with mean 0 and a variance 10⁶. A functional uniform prior will be used for ED₅₀ and h (Bornkamp, 2014), where the prior density for the functional uniform prior is based on all the parameters in the model. However, if a prior distribution appears not to be truly non-informative then alternative prior distributions may be used. An inverse gamma prior with shape of 0.001 and scale of 0.001 will be used for the residual variance (σ^2).

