Once the dose response model has been fitted, the posterior distribution of model parameter ED50 will be summarized through mean, standard deviation and equal-tailed 95% credible intervals and the back transformed posterior distribution of model parameters E₀ and E_{max} will be summarised through geometric means, standard deviation on log_e scale and equal-tailed 95% credible intervals.

The following will be calculated from the model:

- For each study intervention: The posterior mean for Max Δ,
- For each active study intervention: The posterior difference in Max Δ for each dose vs placebo (GSK3888130B XX mg – Pooled placebo across cohorts),

These values will then be back transformed to give:

- For each study intervention: The posterior geometric mean for the ratio to baseline (for Max Δ),
- For each active study intervention: The posterior geometric means of the ratio of each active dose to placebo.

Equal-tailed 95% credible intervals will be presented for each of the above back transformed values. The dose response curve will be plotted for the geometric mean for the ratio to baseline (for Max Δ) with 95% credible intervals. The adjusted posterior geometric means and 95% credible intervals from the Bayesian MMRM analysis will also be included on this plot.

[figure not shown]

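### Does overlaying by-visit MMRM means on the Max Δ dose-response curve for Bcl-2 make that plot misleading?

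*SAP*

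**What the plan says.** SAP 4.3.3.2 analyses Bcl-2 expression in T cells (MdFI) in two ways.

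- **MMRM.** After back-transformation the model gives absolute geometric means, ratios to baseline ("The posterior geometric means of the ratio to baseline for each post-baseline visit") and ratios of each dose to pooled placebo, all by visit. These results have their own display: "A line plot of the adjusted posterior geometric means and credible intervals over time will be presented".
- **Dose response, only if judged suitable.** The text says "the following dose-response models will be fitted for maximum change from baseline" on the log scale (Max Δ). The models are a three-parameter Emax and a four-parameter sigmoid Emax, each with participant baseline as a covariate. E0 is labelled as the placebo level. The final model is the one that fits best.

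From the dose-response model the SAP reports the Max Δ ratio to baseline for each intervention and also "The posterior geometric means of the ratio of each active dose to placebo", with 95% credible intervals. For the figure, "The dose response curve will be plotted for the geometric mean for the ratio to baseline" for Max Δ, followed by "The adjusted posterior geometric means and 95% credible intervals from the Bayesian MMRM analysis will also be included on this plot".

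SAP 4.1.1 sets a general default: "Line plots will be produced on absolute values unless otherwise specified".

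**The concern.** The curve has one value per dose, while the MMRM has one per dose and visit. The overlay sentence names neither the visit nor which of the three MMRM outputs is meant. The visible text does not say whether Max Δ is each participant's own extreme or the change at a common visit, nor in which direction.

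The expected effect is inhibition, and the equation is written at participant level, so the natural reading is each participant's largest decrease. With complete data, the mean of participants' minima cannot exceed the mean at any visit. A well-fitting curve would then tend to sit below the MMRM points, and a reader could take the offset for misfit. The same selection of an extreme pulls the dose-zero level below 1 when placebo does nothing, so E0 could be read as a placebo reduction that is not real. The stake is the reading of the main dose-response figure for a biomarker that SAP Section 5 treats as key among the secondary endpoints.

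**Working it through.** The plan gives no figure for Max Δ to reproduce, and the Bcl-2 probability table in Section 5 is blacked out. The check therefore sizes the effect on the reading that favours the concern.

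**Inputs**
- SD of the log ratio to baseline: 0.3, the maximum stated in SAP Section 5; 0.1 and 0.2 are run as assumed smaller values.
- Placebo n = 14 and active n = 6 (SAP Section 5); active n = 3 in cohorts 1 and 2 (five participants at 3:2).
- Post-dose cellular-biomarker samples: about 6 in IV cohorts and 7 in SC cohorts, read from damaged tables in protocol 1.3.2 and 1.3.3.
- Correlation ρ of the log change between visits: not in the documents; 0.5, 0.8 and 0.9 are assumed.

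**Dose-zero level with no effect**

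For J equally correlated visits, E[minimum] = −SD × √(1−ρ) × m, where m is the expected maximum of J standard normals: 1.267 for J = 6 and 1.352 for J = 7. Example for J = 7, SD 0.3, ρ = 0.5: 0.3 × 0.707 × 1.352 = 0.287, and exp(−0.287) = 0.75.

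| SD | J | ρ = 0.5 | ρ = 0.8 | ρ = 0.9 |
|---|---|---|---|---|
| 0.3 | 7 | 0.75 | 0.83 | 0.88 |
| 0.3 | 6 | 0.76 | 0.84 | 0.89 |
| 0.2 | 7 | 0.83 | 0.89 | 0.92 |
| 0.1 | 7 | 0.91 | 0.94 | 0.96 |

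The by-visit ratio to baseline would be 1.00 throughout.

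**Would the gap show?**

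At J = 6 and SD 0.3 the log-scale gap is 0.27, 0.17 and 0.12 for ρ = 0.5, 0.8 and 0.9. The 95% half-width of one visit mean is 1.96 × 0.3/√14 = 0.16 for placebo and 1.96 × 0.3/√6 = 0.24 for n = 6.

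In 20,000 simulated trials per setting (7 visits, t-intervals standing in for credible intervals), the interval at a given visit lay wholly above the observed Max Δ mean as follows:
- placebo: about 96%, 59% and 16% for ρ = 0.5, 0.8 and 0.9;
- six active participants with a sustained true ratio of 0.70: 46%, 14% and 4%;
- three active participants with the same effect: 15%, 7% and 3–4%;
- a broad peak reaching 0.70: 0–15%.

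The offset is mainly a placebo matter. It is usually hidden at active doses.

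**Does it reach the treatment comparison?**

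With no effect, the Max Δ ratio to placebo centres on 1.00. Its 95% interval lies wholly below 1 in about 2.4–2.7% of trials, and coverage is about 95%. The selection shift cancels because both arms carry it. A sustained 0.70 is returned as 0.70. A broad-peak 0.70 is returned as 0.73–0.78, and at SD 0.3 with 6 visits a sharp-peak 0.70 as 0.78–0.83.

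**Dependence on the reading**

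If Max Δ were the signed largest absolute change, the null placebo level would be about 1.00. At one pre-named visit it would be exactly 1.00, and the curve and the MMRM ratio at that visit would estimate the same quantity apart from covariate adjustment.

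**The case for a change.** The strongest case for a change is that the response variable of a model belongs in the SAP. On the natural reading the offset between curve and overlay follows from the definitions, and its size depends on a variability and time course that nobody yet knows. A reader could not separate misfit from offset. At SD 0.3 a null placebo arm could be drawn with a 12–25% reduction. A definition and one summary by dose would cost little.

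Some of this stands. No visit is named, and on the per-participant reading the two quantities differ. The rest is weaker:

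- **Scale.** The sentence directly before the overlay fixes the plot as ratio to baseline, and the MMRM produces that quantity. The absolute-value default in 4.1.1 yields wherever something else is specified.
- **Fit.** The SAP only places the MMRM means on the plot. It gives them no role in judging fit, and model selection is a separate statement.
- **Definition.** The start of the derivations appendix (6.2, ahead of 6.2.2) and Section 4.5.2 are redacted. That Max Δ is undefined cannot be asserted from the public text. I do not claim that the definition is there.
- **E0.** The shift needs a one-directional, per-participant extreme. E0 is also the intercept at a baseline covariate of zero unless that covariate is centred, so the figures above describe the dose-zero level at mean baseline. Calling the dose-zero level of an Emax model placebo is ordinary usage.
- **Alternative display.** Replacing the overlay with Max Δ ratios to placebo would remove the false placebo drop but understate a short-lived effect, as the 0.73–0.83 results show. It exchanges one limitation for another.

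**Conclusion.** No change to the plan is needed. The unnamed visit is a gap that the analysts must fill to draw the figure, and the plot's ratio-to-baseline axis already points to the matching MMRM output. If Max Δ is a per-participant extreme, a footnote saying that the curve should lie below the by-visit means, also on placebo, prevents the misreading.

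The possible size is a dose-zero level of about 0.75 to 0.96 at mean baseline with no placebo effect. That range assumes SDs of 0.1 to 0.3, equal visit correlations of 0.5 to 0.9 and 6 or 7 visits, and it applies only to the largest-decrease reading. It affects how one figure and E0 are read. The MMRM results are untouched, the Max Δ ratio to placebo stays centred on 1.00 under no effect, and no bias in ED50 has been shown. The model is optional, the endpoint secondary, and the study tests no formal hypothesis. Readers who need the size of a short-lived effect have the by-visit MMRM ratios to placebo, which the SAP already provides.

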4.3.4. Target Engagement Biomarker Analyses

4.3.4.1. Main analytical approach

Free IL-7 levels will be derived from total IL-7 concentrations (named as Derived Free IL-7) over time using a nonlinear mixed effects modelling approach by the Clinical Pharmacology Modelling and Simulation (CPMS) department as described in Section 4.4.5. Summary outputs (geometric mean and 95% CIs) for derived free IL-7 inhibition will be reported by CPMS, separately to those outputs in the OPS but listed/cross-referenced in the CSR.

CCI [REDACTED]

[figure not shown]
CCI

CONFIDENTIAL

213960

CCI

[figure not shown]
CCI

CCI

[figure not shown]
CCI

CONFIDENTIAL

213960

[figure not shown]
CCI

[figure not shown]
CONFIDENTIAL

213960

CCI

[figure not shown]
CCI

[figure not shown]
CONFIDENTIAL

213960

CCI

CCI

CCI

4.5. Other Analyses

4.5.1. Subgroup analyses

No formal subgroup analyses are planned.

4.5.2. Other variables and/or parameters

CCI

4.6. Dose Escalation

The Dose Escalation Plan describes the responsibilities, conduct of the DEC and how the integrity of the study, including blinding, will be maintained.

The site will provide safety reports (including CD4⁺ T cell counts) for each dose escalation. CPMS will provide PK outputs including PK profiles and derived PK parameters from non-compartmental PK data analysis as permitted by data.

Additionally, study Statistics and Programming team members will provide outputs for each DEC meeting. describes the details of the analyses and outputs reviewed in the Dose Escalation meetings.

4.7. Interim Analyses

- **Interim Analysis – 1**

The first Interim Analysis will be performed once a minimum of four participants dosed with GSK3888130B in cohort 4 have completed up to and including the Day CCI visit.

During this interim analysis, safety data (including CD4⁺ T cells counts), immunogenicity, PD biomarker T cell Bcl-2, TE total IL-7 levels and PK data will be reviewed.

Most of the outputs will be provided during the Cohort 4 DEC meeting. Additionally, study Statistics and Programming team members will provide Immunogenicity, Total IL-7 and PD biomarker T Cell Bcl-2 outputs for review. describes the details of the analyses and outputs that will be provided for this interim analysis.

CCI

CCI [REDACTED]

[REDACTED]

- **Interim Analysis – 2**

The second Interim Analysis will be performed once all participants in cohort 6 have completed up to and including the Day CCI visit for PK, TE total IL-7 levels, PD secondary endpoint T cell Bcl-2, CCI [REDACTED], CCI [REDACTED] and up to and including Day CCI for safety endpoints.

During this interim analysis, selected study population, safety data (including CD4⁺ T cells counts), immunogenicity, PK, TE total IL-7 levels, PD secondary endpoint T cell Bcl-2, cellular biomarkers, CCI [REDACTED] [REDACTED] [REDACTED], CCI [REDACTED] [REDACTED] [REDACTED] [REDACTED] [REDACTED] [REDACTED] will be reviewed. describes the details of the analyses and outputs that will be provided for this interim analysis.

- **Early Data Extraction to CPMS**

CPMS will access unblinded data earlier than Interim Analysis – 2 reporting for the derivation of free IL-7 named as ‘Derived Free IL-7 and for PK/PD modelling to support dose selection in future studies as detailed in the Section 4.4.5. GSK Biostatistics will share PK concentrations and total IL-7 data with CPMS via the HARP system and the Randomization Office team will share randomization schedules upon request from GSK Biostatistics. Participants’ body weight data will be provided by Data management. Bcl-2 data will be accessed from External Alliance Portal (EAP) by CPMS.

Table 3 Summary of Dose Escalation and Interim Analysis

Deliverables	Domain	Outputs
Each DEC	TE	Summary plot of Total IL-7 Levels by dose (if data is available)
Interim Analysis – 1	1. Immunogenicity 2. PD 3. TE	1. Summary of Immunogenicity Results 2. Listing of Immunogenicity Results (only if positive immunogenicity results) 3. Summary plot of T Cell Bcl-2 data 4. Summary plot of Total IL-7 data
Interim Analysis - 2	1. Study Population 2. Safety (including CD4+ cell counts) 3. Immunogenicity	Detailed list of outputs mentioned in OPS

Deliverables	Domain	Outputs
	4. PK 5. PD Secondary endpoint (Bcl-2 T Cell) 6. TE (Total IL-7) 7. CCI [REDACTED] [REDACTED] 8. CCI [REDACTED] 9. CCI [REDACTED] 10. CCI [REDACTED] 11. CCI [REDACTED] 12. CCI [REDACTED]	

Note: The subset of CCI [REDACTED] endpoints will be descriptively summarized and plotted by GSK Biostatistics based on internal review and will be included in the second Interim analysis.

4.8. Changes to Protocol Defined Analyses

[figure not shown]
There were no changes or deviations to the originally planned statistical analysis specified in the protocol amendment 2 (Dated: 10-FEB-2022).

5. SAMPLE SIZE DETERMINATION

[figure not shown]
Approximately 54 participants will be recruited to seven single ascending dose cohorts. Five participants will be randomized to either GSK3888130B or placebo in 3:2 ratio in cohorts 1 and 2. Eight participants will be randomized to either GSK3888130B or placebo in 3:1 ratio in all other cohorts, **CCI**

No formal statistical techniques were used to calculate the sample size for this study; it has been determined to allow preliminary assessment of safety, tolerability, PK and PD. However, as a key secondary endpoint, considerations has been given to the ratio to baseline of the PD biomarker Bcl-2. It is assumed that this endpoint is \log_e normally distributed. Based on 6 participants from the highest GSK3888130B dosed cohort and 14 placebo participants pooled across all cohorts, the probability of different true inhibition (GSK3888130B vs. placebo) thresholds of interest is given in the table below. A non-informative prior distribution and a maximum between participant SD (\log_e scale) of 0.3 is assumed for both GSK3888130B and placebo arms.

[figure not shown]
CCI

CCI

[figure not shown]
CCI

CONFIDENTIAL

213960

CCI

6. SUPPORTING DOCUMENTATION

6.1. Appendix 1 Study Population Analyses

A summary of the number of participants in each of the participant level analysis set will be provided.

6.1.1. Participant Disposition

A summary of the number and percentage of participants who completed the study as well as those who prematurely withdrew from the study will be provided. Reasons for study withdrawal will be summarized.

6.1.2. Demographic and Baseline Characteristics

The demographic characteristics including age, gender, ethnicity, height/weight at screening and race will be summarized with descriptive statistics. In addition, the following age categories will be summarized: 18-64, 65-84 and >=85 based on the Enrolled Analysis Set.

6.1.3. Protocol Deviations

Important protocol deviations will be summarized.

Protocol deviations will be tracked by the study team throughout the conduct of the study. These protocol deviations will be reviewed to identify those considered as important as follows:

- Data will be reviewed prior to unblinding and freezing the database to ensure all important deviations (where possible without knowing the study intervention details) are captured and categorised in the protocol deviations dataset.
- The Statistics and Programming team will review any treatment deviations after unblinding and will notify the study team. This is also captured and categorised in the protocol deviations dataset.
- This dataset will be the basis for the summaries of important protocol deviations.

In addition to the overall summary of important protocol deviations, separate summaries will be produced for important protocol deviations related to COVID-19, and important protocol deviations not related to COVID-19 respectively.

Visits and assessments missed due to the COVID-19 pandemic, together with visits conducted remotely, will be summarized.

